10. MANAGEMENT OF TOXICITY AND COMPLICATIONS

10.1. Guidelines for Management of Potential Adverse Events

Subjects will be monitored for AEs from the time of signing informed consent through 30 days after the date of the last dose of cabozantinib treatment. Subjects will be instructed to notify their physician immediately at the onset of any AE. Seriousness, severity grade, and relationship to study treatment of AEs will be determined by the investigator. AE severity will be graded by the investigator in accordance with CTCAE v.5.0.

Management of severe or intolerable adverse reactions may require temporary dose reduction and/or interruption for cabozantinib.

10.2. Cabozantinib Related Toxicity

10.2.1. Dose-Limiting Toxicity

The most frequent AEs experienced by $\geq 20\%$ of subjects treated with cabozantinib in descending order of frequency were diarrhea, fatigue, decreased appetite, nausea, weight decreased, PPES, vomiting, constipation, hypertension, dysgeusia, dysphonia, asthenia, and dyspnea. For a full description of the safety profile of cabozantinib, refer to the cabozantinib Investigator's Brochure.

Other medically important but less frequent AEs including arterial thrombotic AEs (e.g., transient ischemic attack [TIA], and myocardial infarction [MI]) and venous thrombotic AEs (e.g., deep vein thrombosis [DVT] and pulmonary embolism), severe hemorrhagic events, proteinuria, wound healing complications, gastrointestinal (GI) perforation, abscesses including intra-abdominal and pelvic abscess, GI and non-GI fistula formation, osteonecrosis, and reversible posterior leukoencephalopathy syndrome (RPLS).

Adverse events associated with laboratory abnormalities experienced by $\geq 5\%$ of subjects treated with cabozantinib in descending order of frequency were anemia, AST increased, ALT increased, hypothyroidism, hypokalemia, hypomagnesemia, thrombocytopenia, hypocalcemia, hypophosphatemia, lactate dehydrogenase (LDH) increased, lipase increased, neutropenia, hyponatremia, ALP increased, leukopenia, and hyperglycemia.

Adverse events may occur within the first few weeks during treatment with cabozantinib, as cabozantinib is expected to reach steady state exposure at approximately 2 weeks following first dose. Events that generally have an early onset include hypocalcemia, hypokalemia, thrombocytopenia, hypertension, PPES, abdominal pain, mucosal inflammation, constipation, diarrhea, and vomiting. Adverse events should be managed with supportive care at the earliest signs of toxicity. Dose reductions and treatment interruptions should be considered. Dose reductions are recommended for events that, if persistent, could become serious or intolerable.

Cabozantinib should be discontinued for the following AEs: visceral perforation or fistula formation, severe hemorrhage, serious arterial thromboembolic events, nephrotic syndrome, hypertensive emergency, persistent uncontrolled hypertension despite optimal medical management, and RPLS.

Determination and attribution of DLT are critical for determining the RP2D for this study. The DLT period will include all subjects enrolled to the phase 1 component of the study who receive cabozantinib in combination with radiation therapy. The DLT period is defined as beginning on C1D8 and continuing until 28 days after completion of concurrent radiation therapy and cabozantinib. Cabozantinib is anticipated to have systemic effects at sites distant from that receiving neoadjuvant radiation treatment. It may also interact loco-regionally at the site of radiation administration. However, as the objective of this study is to assess the impact of the cabozantinib/radiotherapy combination, only those effects in the region subject to radiation therapy are considered pertinent and will be considered DLT.

DLT are defined as any Grade 3 or greater AE, occurring in the region subject to radiation therapy, at least possibly related (per investigator attribution) to concurrent radiation therapy and cabozantinib therapy. Toxicities with a clearly identified and documented alternative explanation may be deemed non-DLT. Toxicities which are clearly identified and documented as related to cabozantinib therapy only or radiation therapy only may be deemed non-DLT. Only toxicities observed in the region subject to radiation therapy will be considered DLT.

Toxicities that are Grade 3 or greater that meet the following will always be considered DLT:

1. Occur after the initiation of concurrent cabozantinib/radiation therapy until 28 days after completion of radiation therapy;
 - a. Involve the region of a subject's body that is receiving concurrent radiation therapy; and
 - b. Are of a degree or character inconsistent with anticipated radiation effects.

Dose modification guidelines are outlined in Table 5, Table 6, and Table 8 for clinically significant toxicities that are deemed to have a relation to cabozantinib. Clinically significant toxicities that are deemed to have a relationship to radiation therapy only will be managed per standard institutional practice, additional information is available in Section 10.3.

10.2.2. Adverse Event Management Algorithms

Table 8 - Management Guidelines for Adverse Events Possibly Related to Cabozantinib

System/Organ	Adverse Event	CTCAE Grade v5.0	Dose modification Algorithm
Skin/Mucosa	Palmar-plantar Erythrodysesthesia Syndrome	Grade 1	If PPES is clinically insignificant and tolerable, cabozantinib may be continued at current dose, otherwise reduce by one dose level. Urea 20% cream twice daily and Clobetasol 0.05% cream once daily to be reassessed at least weekly. If PPES does not improve, or worsens after 2 weeks, follow intervention guidelines for grade 2.
		Grade 2	Cabozantinib treatment may be continued if PPES is tolerated. Cabozantinib should be dose reduced or interrupted if PPES is intolerable. Continue urea 20% cream twice daily AND high potency steroid cream (e.g., clobetasol 0.05%) once daily and add analgesics (e.g., NSAIDs/gamma-aminobutyric acid agonists) for pain control if needed. Reassess at least weekly; if PPES worsens or affects self-care, proceed to the intervention guidelines for Grade 3.
		Grade 3+	Interrupt cabozantinib treatment until severity decreases to Grade 1 or 0. Continue treatment of skin reaction with high potency steroid cream (e.g., clobetasol 0.05%) twice daily AND analgesics. Resume study drug at a reduced dose if PPES recovers to Grade ≤ 1. Discontinue subject from study treatment if PPES does not improve within 6 weeks.

	Stomatitis and/or Mucositis	Any Grade	
No change in cabozantinib treatment. Preventive measures may include a comprehensive oral examination to identify and treat any potential risk for complications before study treatment is initiated. Appropriate correction of local factors should be instituted as indicated, such as modification of ill-fitting dentures and appropriate care of gingivitis. During treatment with cabozantinib, good oral hygiene and standard local treatments such as non-traumatic and non-irritating cleansing, and oral rinses (e.g., with a weak solution of salt and baking soda) should be maintained. Lips should be kept moisturized with lip balm. The use of lipstick, lip-gloss, and Vaseline should be avoided.
 
Local treatment should be instituted at the earliest onset of symptoms. Obtain bacterial/viral culture if oral infection is suspected and treat infection as clinically indicated.

Lab Abnormalities	Proteinuria	UPC Ratio \leq 1 mg/mg (\leq 113.1 mg/mmol)	
No change in cabozantinib treatment or monitoring

		For UPC Ratio >1 and <3.5 mg/mg (>113.1 and <395.9 mg/mmol)	
Consider confirming with a 24-h protein assessment within 7 days
 
No change in cabozantinib treatment required if UPCR \leq 2 mg/mg or urine protein \leq 2 g/24 h on 24-h urine collection.
 
Dose reduce or interrupt cabozantinib treatment if UPCR $>$ 2 mg/mg on repeat UPCR testing or urine protein $>$ 2 g/24 h on 24-h urine collection.
 
Continue cabozantinib on a reduced dose if UPCR decreases to $<$ 2 mg/mg.

		
Consider interrupting cabozantinib treatment if UPCR remains $> 2 \text{ mg/mg}$ despite a dose reduction until UPCR decreases to $< 2 \text{ mg/mg}$. Restart cabozantinib treatment at a reduced dose after a dose interruption.
 
Repeat UPCR within 7 days and once per week. If UPCR $< 1 \text{ mg/mg}$ on 2 consecutive readings, UPCR monitoring can revert to protocol-specific times. (Second reading is confirmatory and can be done within 1 week of first reading.)
 
If UPCR remains $> 1 \text{ mg/mg}$ and $< 2 \text{ mg/mg}$ for 1 month or is determined to be stable (< 20% change) for 1 month, check urine protein/creatinine per protocol or as clinically indicated.

	UPC Ratio $\geq 3.5 \text{ mg/mg}$ ($\geq 395.9 \text{ mg/mmol}$)	
Interrupt cabozantinib treatment pending repeat UPCR within 7 days and/or 24 h urine protein.
 
If $\geq 3.5 \text{ mg/mg}$ on repeat UPCR, continue to interrupt cabozantinib treatment and check UPCR every 7 days. If UPCR decreases to $< 2 \text{ mg/mg}$, restart cabozantinib treatment at a reduced dose and monitoring of urine protein/creatinine should continue weekly until the UPCR decreases to $< 1 \text{ mg/mg}$.
 
If UPCR remains $> 1 \text{ mg/mg}$ and $< 2 \text{ mg/mg}$ for 1 month or is determined to be stable (< 20% change) for 1 month, check urine protein/creatinine per protocol or as clinically indicated.

	Nephrotic Syndrome	Discontinue cabozantinib.

	Elevated Aminotransferases (ALT/AST)	Grade 3 or 4	
Interrupt cabozantinib treatment if ALT/AST elevations are also accompanied by progressive elevation of total bilirubin and/or elevations of coagulation tests.
 
Transaminases should be monitored weekly if elevated to Grade 3+, in combination with total bilirubin and coagulation tests.
 
Cabozantinib should be discontinued if hepatic dysfunction does not resolve to Grade 1 or better within two weeks of interrupting therapy.
 
Elevations $>3 \times$ ULN of ALT or AST concurrent with $>2 \times$ ULN total bilirubin without other explanation (such as initial findings of cholestasis and obstructive disease, viral hepatitis, pre-existing or acute liver disease, or another drug capable of causing the observed injury) can indicate drug-induced liver injury (DILI) and study drug should be permanently discontinued.

Cardiac Toxicity	Hypertension	Grade 2 (Systolic 140-159 or	Optimize antihypertensive medications by adding new or additional antihypertensive medications and/or increase dose of existing medications.

	Diastolic 90-99)	Reduce cabozantinib treatment by one dose level if optimal antihypertensive therapy (usually to include 3 agents) does not result in BP <150 mm Hg systolic or <100 mm Hg diastolic If subject is symptomatic interrupt cabozantinib treatment
	Grade 3 (Systolic \geq 160 or Diastolic \geq 100)	Reduce cabozantinib by one dose level or interrupt cabozantinib treatment per investigator discretion Add new or additional anti-hypertensive medications and/or increase dose of existing medications and monitor subject closely for hypotension. If optimized antihypertensive therapy (usually to include 3 agents) does not result in BP < 150 mm Hg systolic or < 100 mm Hg diastolic, cabozantinib treatment should be dose reduced further or interrupted Cabozantinib treatment should be dose interrupted if upper limits of systolic BP (\geq 160 mm Hg) are sustained and not adequately manageable or if systolic BP is > 180 mm Hg or diastolic BP > 110 mm Hg, or if subject is symptomatic Re-start cabozantinib treatment at the most tolerable dose only if BP falls to and is sustained at < 150 mm Hg systolic and < 100 mm Hg diastolic
	Grade 4	Permanently discontinue cabozantinib
Arterial Thromboembolic Events	Any Grade	Discontinue cabozantinib.
ECG QTc (QT Corrected)	Grade 3	Perform two additional ECGs not less than 3 minutes apart, within 30 minutes after the initial ECG. If the average of the QTcF of the three ECGs

	Interval Prolonged		
is >500ms, interrupt cabozantinib treatment. Symptomatic subjects should be hospitalized for a thorough cardiology evaluation.
 
Regardless of symptom presentation, check magnesium, potassium, and calcium levels, correcting as clinically indicated. Repeat ECG triplicates hourly until average QTcF is <500ms, or otherwise determined by consultation with cardiologist or appropriate expert.
 
Cabozantinib treatment should be interrupted for a minimum of 1 week following the return of the QTcF to <500ms. Cabozantinib treatment may be resumed at one dose level reduction. Following reinitiation of study treatment, ECGs must be repeated weekly for 2 weeks, then every 2 weeks for 1 month, then may return to the regularly defined timepoints.
 
If there are development of prolonged symptoms that are the result of QT interval prolongation or if a recurrence of QTcF prolongation occurs after reinitiation of treatment at a reduced dose, cabozantinib should be permanently discontinued.

	Grade 4		Discontinue cabozantinib.
Gastrointestinal Disorders	Diarrhea	Grade 1-2 lasting < 48h	
Continue with study treatment and consider dose reduction
 
Initiate treatment with an antidiarrheal agent (e.g., loperamide 4 mg followed by 2 mg after each episode of diarrhea [maximum: 16 mg loperamide per day])
 
Dietary modifications (e.g., small lactose-free meals, bananas and rice)
 
Intake of isotonic fluids (1-1.5 L/day)
 
Re-assess after 24 hours:

			
 • Diarrhea resolving to baseline bowel habits: gradually add solid foods and discontinue or decrease antidiarrheal treatment after 12 h diarrhea-free interval • Diarrhea not resolving: Continue/resume antidiarrheal treatment and hold cabozantinib therapy until diarrhea resolves to Grade 1 or Baseline
	Grade 2 lasting >48h, Grade 3		
Interrupt study treatment
 
Rule out infection (e.g., stool sample for culture)
 
Administer antibiotics as needed (e.g., if fever or Grade 3-4 neutropenia persists > 24 h)
 
Administer fluids (1-1.5 L/day orally or IV, as appropriate) for hydration or to correct electrolyte abnormalities
 
For Grade 3-4 or complicated lower grade diarrhea consider hospitalization and IV hydration
 
Diarrhea resolving to baseline bowel habits or Grade ≤ 1: consider restarting study treatment at reduced dose
 
Diarrhea not resolving: Start and/or continue antidiarrheal treatment (e.g., loperamide 4 mg followed by 2 mg after each episode of diarrhea [maximum: 16 mg loperamide per day]). Consider starting second line antidiarrheal or referral to gastroenterologist

	Grade 4		Permanently discontinue cabozantinib
Fistula, perforations, bowel	Any Grade		For any grade perforation of any organ, GI leak, or any fistula, discontinue cabozantinib.

	obstruction, intra-abdominal and pelvic abscesses		For any grade bowel obstruction requiring medical intervention, delay cabozantinib until obstruction resolves completely, and then resume cabozantinib at the previous dose. For obstruction requiring surgery delay cabozantinib until full recovery from surgery, then resume cabozantinib at the previous dose.
Other	Reversible Posterior Leukoencephalopathy Syndrome	Any Grade	Permanently discontinue cabozantinib
	Nervous System Disorders (Other)	Any Grade	Cabozantinib appears to represent minimal risk of adverse neurological effects based on nonclinical Good Laboratory Practice (GLP)-compliant toxicology studies. Dysphonia, dysgeusia, headache, dizziness, confusional state, convulsion, depression, memory impairment, hypoesthesia, peripheral neuropathy, insomnia, ataxia, and encephalopathy have been observed in clinical studies with cabozantinib. The development of any new or progressive, unexplained neurological symptoms should be assessed for underlying causes.
	Non-CNS, Non-Pulmonary bleeding	Grade 2	Delay cabozantinib until \leq grade 1, then resume with one dose level reduction.
		Grade 3 or 4	Permanently discontinue cabozantinib
	Fistula, perforations, bowel obstruction, or wound dehiscence	Any Grade	For any grade perforation of any organ, GI leak, or any fistula, discontinue cabozantinib. For any grade bowel obstruction requiring medical intervention, delay cabozantinib until obstruction resolves completely, and then resume cabozantinib at the previous dose. For obstruction requiring surgery delay

			
cabozantinib until full recovery from surgery, then resume cabozantinib at the previous dose.
 
For wound dehiscence requiring medical or surgical intervention discontinue cabozantinib.
 
Complications from radiation therapy especially of the thoracic cavity including mediastinum have been identified as a possible predisposing risk factor for non-GI fistula formation in subjects undergoing treatment with VEGF pathway inhibitors.
 
Discontinue cabozantinib and initiate appropriate management in subjects who have been diagnosed with a non-GI fistula.

	Wound healing and surgery	Any Grade	
Cabozantinib has the potential to cause wound healing complications and wound dehiscence which may even occur long after a wound has been considered healed. Therefore, surgical and traumatic wounds must not only be completely healed prior to starting cabozantinib treatment but must also be monitored for wound dehiscence, wound infection and other signs of impaired wound healing while the subject is being treated with cabozantinib. If dehiscence occurs, cabozantinib treatment should not be restarted until complete healing has taken place.
 
Treatment with cabozantinib should be stopped at least 28 days prior to scheduled surgery. The decision to resume treatment with cabozantinib after surgery should be based on clinical judgment of adequate wound healing.

	Hemorrhage	Any Grade	
Hemorrhagic events, including serious and sometimes fatal events, have been reported with cabozantinib. Subjects should be monitored for bleeding events with serial complete blood counts and physical

			
examination while on study. The risk of hemorrhage in cabozantinib-treated subjects with brain metastases has not been thoroughly analyzed. Subjects enrolled with treated and stable brain metastases should be monitored with a high index of suspicion if symptoms that could be due to a CNS hemorrhage occur.
 
Cabozantinib should be discontinued in subjects with serious and life-threatening bleeding events or recent hemoptysis (≥ 2.5 mL of red blood).

	Thromboembolic event	Any Grade	
Subjects who develop a pulmonary embolism and/or DVT should have study treatment interrupted until therapeutic anticoagulation is established.
 
Treatment with cabozantinib may be resumed in subjects with pulmonary embolism or DVT if it is determined that the event is uncomplicated and that the subject is deriving clinical benefit from cabozantinib treatment and that anticoagulation does not place them at a significant risk that outweighs the benefit of resuming treatment.
 
Low molecular weight heparins are the preferred management for thrombotic events.
 
Oral anticoagulants (e.g., warfarin or other coumarin-related agents, direct thrombin or direct FXa inhibitors, or antiplatelet agents, or chronic use of aspirin above low dose levels for cardioprotection per local applicable guidelines) are not allowed.
 
Further treatment with cabozantinib should be discontinued in subjects who develop an acute MI, cerebral infarction, or any other clinically significant arterial thromboembolic complication.

	Osteonecrosis	Any Grade	
Osteonecrosis of the jaw (ONJ) occurred in <1% of subjects treated with cabozantinib. ONJ can manifest as jaw pain, osteomyelitis, osteitis, bone erosion, tooth or periodontal infection, toothache, gingival ulceration or erosion, persistent jaw pain or slow healing of the mouth or jaw after dental surgery.
 
Perform an oral examination prior to initiation of cabozantinib and periodically during cabozantinib treatment. Advise subjects regarding good oral hygiene practices. Withhold cabozantinib treatment for at least 28 days prior to scheduled dental surgery or invasive dental procedures, if possible. Withhold cabozantinib for development of ONJ until complete resolution.

	Infections and/or Infestations	Any Grade	
Infections are commonly observed in cancer subjects. Predisposing risk factor include a decreased immune status (e.g., after myelosuppressive anticancer therapies, splenectomy), destructive growth of the underlying malignancy including bone marrow infiltration with suppression of normal hematopoiesis, as well as the presence of IV devices.
 
Infections and abscesses should be treated with appropriate local care and systemic therapy. Cabozantinib should be interrupted until adequate healing has taken place.

	Blood and Lymphatic System Disorders	Any Grade	
Hematological toxicities (i.e., neutropenia and thrombocytopenia) and associated complications have been observed after administration of cabozantinib and may be managed with dose interruptions and/or dose reductions. Subjects with hematologic toxicities may require additional or more frequent laboratory tests according to institutional guidelines.

			Dose reductions or dose interruptions for hematological toxicities are not mandated but can be applied as clinically indicated. Supportive care for thrombocytopenia or anemia, such as transfusions, may be managed according to institutional guidelines. The use of colony-stimulating growth factors should be considered. Febrile neutropenia or evidence of infection associated with neutropenia must be assessed immediately and treated appropriately and in a timely manner according to institutional guidelines.
Fatigue	Any Grade		Common causes of fatigue, such as anemia, deconditioning, emotional distress (depression and/or anxiety), poor nutrition, dehydration, sleep disturbance, and hypothyroidism should be ruled out and treated according to standard of care. Pharmacological management should be considered after disease specific morbidities have been excluded when not prohibited.
Weight Loss	Any Grade		Anorexia and weight loss should be managed according to local standard of care including nutritional support. Pharmacologic therapy should be considered for appetite enhancement when not prohibited by a protocol.
Electrolyte Disorders	Any Grade		Serum electrolyte disorders including hyponatremia, hypokalemia, hypomagnesemia, and hypophosphatemia have been reported during treatment with cabozantinib, and serum electrolyte levels should be monitored frequently while receiving cabozantinib. Clinically relevant electrolyte disorders should be managed according to the dose modification guidelines as clinically indicated. Standard clinical practice guidelines should be used for management of electrolyte disorders and may include oral or intravenous replacement.

	Endocrine Disorders	Any Grade	Treatment-emergent elevation of thyroid-stimulating hormone (TSH) has been observed with cabozantinib treatment. Currently available data are insufficient to determine the mechanism of thyroid function test alterations and its clinical relevance. Management of thyroid dysfunction (e.g., symptomatic hypothyroidism) should follow accepted clinical practice guidelines.
	Angioedema	Any Grade	Angioedema should be managed according to standard practice. The subject should be observed until symptoms resolve, with attention to maintaining an open airway.
	Other Non-Hematologic Grade 3 or 4 Toxicity	Grade 3 or 4	For other grade 3 or 4 non-hematologic toxicity not described above, (excluding nausea, vomiting, and diarrhea; unless refractory to anti-emetics and/or antidiarrheals) and considered at least possibly related to treatment, delay cabozantinib treatment until toxicity improves to \leq grade 1, then resume treatment with one dose level reduction.

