7.1.2. Cabozantinib Dose Modification and Stopping Rules

The following should be taken into consideration in decisions regarding dose modifications (reductions or interruption):

- As a general approach all AEs should be managed with supportive care at the earliest signs of toxicity considered related to the study treatment. Should this be ineffective, dose interruptions and/or reductions should be considered to prevent worsening of toxicity.
- The assigned starting dose for cabozantinib is 40 mg/day. The dose level may go to -1 as seen in Table 4. Further dose reductions beyond 20 mg daily are not permitted.
- Dose modification criteria for cabozantinib are shown in Table 5 and 6. Dose interruptions and/or reductions should be implemented for unacceptable toxicity. Doses may be modified at any time while a subject is on treatment.

- Dose reductions or interruptions may also occur in the setting of lower grade toxicity if the investigator feels it is in the interest of a subject's safety and will optimize drug tolerability.
- Interruption of cabozantinib treatment for cabozantinib-related AEs may occur at any time per investigator discretion. If treatment is interrupted due to related AEs for more than 6 weeks, cabozantinib should be discontinued.

Dose interruptions for reason(s) other than treatment-related AEs (e.g., surgical procedures, upper respiratory infection, common cold) can be longer than 6 weeks per the discretion of the investigator.

Guidelines for the management of specific AEs are provided in Section 10.2.2.

Table 5 - Dose Modifications of Cabozantinib

Assigned Dose	First Dose Level Reduction	Second Dose Level Reduction
60-mg cabozantinib oral qd*	40-mg cabozantinib oral qd	20-mg cabozantinib oral qd
40-mg cabozantinib oral qd	20-mg cabozantinib oral qd	No further dose reductions
20-mg cabozantinib oral qd**	No further dose reductions	No further dose reductions

*qd, once daily

**Cabozantinib will be discontinued if a qd dose of 20-mg cabozantinib daily (minimum dose) is not tolerated

Table 6 - Dose Modifications of Cabozantinib for Treatment-Related AEs

CTCAE v.5.0 Grade	Recommended Guidelines for Management ^a
Grade 1 AEs	Add supportive care as indicated. Continue cabozantinib treatment at the current dose level if AE is manageable and tolerable.
Grade 2 AEs which are tolerable and are easily managed	Continue cabozantinib treatment at the current dose level with supportive care.

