Grade 2 AEs which are intolerable and cannot be adequately managed	At the discretion of the investigator, cabozantinib should be dose reduced or interrupted. Note: It is recommended that dose holds be as brief as possible.

Grade 3 AEs (except clinically non-relevant laboratory abnormalities)	Cabozantinib should be interrupted unless the toxicity can be easily managed with a dose reduction and optimal medical care. Note: It is recommended that dose holds be as brief as possible.
Grade 4 AEs (except clinically non-relevant laboratory abnormalities)	Subjects should have cabozantinib interrupted immediately. Discontinue cabozantinib unless the following criteria are met: 
• Subject is deriving clear clinical benefit as determined by the investigator• Toxicity can be managed with a dose reduction following recovery to Grade 1 (or baseline) and optimal medical care

Note: The dose delay and modification criteria for specific medical conditions are provided in Section 10.2.2.

^a Study treatment dose adjustment is only needed if the toxicity was deemed related to cabozantinib treatment or had an unclear relationship to cabozantinib treatment.

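### Table 8 tells sites to leave cabozantinib unchanged for stomatitis or mucositis of any grade, which conflicts with Table 6 at intolerable Grade 2, Grade 3 and Grade 4

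*Combined protocol and SAP*

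**What the plan says.** Table 8 (Section 10.2.2) has a single row for stomatitis and/or mucositis. Its grade label is Any Grade, and its entry in the dose-modification column begins "No change in cabozantinib treatment. Preventive measures may include a comprehensive oral examination to identify and treat any potential risk". The rest of the entry is preventive and local oral care. It contains no grade split, tolerability condition or escalation step.

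Table 6 (Section 7.1.2) sets dose actions by grade for events related to cabozantinib or of unclear relationship to it:

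- Grade 1: continue at the current dose if manageable and tolerable.
- Tolerable Grade 2: "Continue cabozantinib treatment at the current dose level with supportive care".
- Intolerable Grade 2: "At the discretion of the investigator, cabozantinib should be dose reduced or interrupted".
- Grade 3: "Cabozantinib should be interrupted unless the toxicity can be easily managed with a dose reduction and optimal medical care".
- Grade 4: "Subjects should have cabozantinib interrupted immediately. Discontinue cabozantinib unless the following criteria are met". The criteria are clear clinical benefit and toxicity that can be managed with a dose reduction after recovery.

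Section 10.2.1 ties the tables together: "Dose modification guidelines are outlined in Table 5, Table 6, and Table 8 for clinically significant toxicities". It gives no order of precedence.

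**The concern.** A clinician facing intolerable Grade 2, Grade 3 or Grade 4 mucositis attributed to cabozantinib finds two dose guidelines of equal standing that give different instructions. One says to leave the dose alone. The other says to reduce or interrupt and, at Grade 4, to stop immediately. A site that follows the event-specific row literally would keep a subject with severe mucosal toxicity on full dose.

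The event is foreseeable, since Section 10.2.1 names mucosal inflammation among the early-onset effects of the drug. What is at stake is subject safety and consistent dose handling. The efficacy inference is not affected.

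**Working it through.** No figure in the plan is in dispute, so the check compares the text grade by grade and then looks for a rule that settles the difference.

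**Same events in scope.** Table 8 is for events possibly related to cabozantinib. Table 6 is for events related or of unclear relationship. A drug-related mucositis falls under both. Table 6's carve-out at Grades 3 and 4 is for laboratory findings without clinical relevance, so it does not cover mucositis.

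**Comparison.**

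| Level | Table 8 row | Table 6 | Result |
|---|---|---|---|
| Grade 1 | no change | continue | agree |
| Grade 2, tolerable | no change | continue | agree |
| Grade 2, intolerable | no change | reduce or interrupt, at investigator discretion | conflict (soft) |
| Grade 3 | no change | interrupt, or manage with a reduction | conflict |
| Grade 4 | no change | interrupt at once; discontinue unless criteria are met | conflict |

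Agreement 2, conflict 3, total 2 + 3 = 5 rows. This counts table rows and is not a measure of risk. At Grade 3 both options in Table 6 change treatment, so neither can be reconciled with no change.

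**Is there a rule that settles it?**

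- Section 10.2.1 names the three tables side by side with no precedence.
- The last row of Table 8 would delay and then reduce the dose, but it opens "For other grade 3 or 4 non-hematologic toxicity not described above". Stomatitis/mucositis is described above it, so that row does not reach it.

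**Is the row an outlier within Table 8?** A no-change instruction appears three times. The two proteinuria entries are bounded by severity: one applies at a urine protein/creatinine ratio of at most 1 mg/mg, and the other ("No change in cabozantinib treatment required if UPCR") at a ratio of at most 2 mg/mg. The stomatitis/mucositis entry is the only one of the three without a bound. The neighbouring row for palmar-plantar erythrodysesthesia, in the same organ group, is split by grade and requires interruption from Grade 3.

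**What limits the harm?** Adverse events are assessed on Days 1, 8 and 15 of Cycles 1 to 3 (Sections 6.2.2 to 6.2.4), which is 3 × 3 = 9 scheduled assessments. Cycle 1 Day 1 precedes the first dose, so 9 − 1 = 8 fall on drug. From Cycle 4 visits are on Day 1 only (Table 2). Stomatitis/mucositis is not in Section 10.2.1's list of events seen in at least 20% of subjects. No rate by grade is given.

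**The case against.** The best argument on the other side is that Section 7.1.2, in its text and in the note under Table 6, sends the reader to Section 10.2.2 for specific events. On that view Table 6 is the default and Table 8 the deliberate exception. Table 8 does depart from Table 6 elsewhere: isolated transaminase elevations, hematologic toxicity (where dose changes are optional) and bowel obstruction (where the previous dose is resumed) are all handled differently.

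The cross-references do exist, but they are pointers and do not say that Table 8 overrides Table 6. If Table 8 did govern, its instruction for Grade 4 mucositis would be no dose change. That cannot be squared with Section 7.1.2, which directs interruption or reduction for unacceptable toxicity, or with Section 10.2.1, which recommends reduction for events that may become serious or intolerable if they persist. The other departures do not help either. The hematologic row leaves dose changes open, the obstruction row delays treatment first, and the transaminase row sets conditions for interruption. None of them instructs that treatment stay unchanged at every grade.

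Parts of the objection stand. The intolerable Grade 2 conflict is soft, because Table 6 leaves the action to the investigator. Investigators may interrupt cabozantinib for related events at any time (Section 7.1.2). Section 10.1 anticipates dose action for severe or intolerable reactions. Section 13.1 requires discontinuation when the investigator judges that an event warrants it, and when toxicity has not recovered to tolerable Grade 2 or better within 6 weeks, unless the subject is clearly benefiting. These points reduce the likely harm but do not make the row correct.

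**Conclusion.** The concern holds. The stomatitis/mucositis row is wrong as written whichever table is taken to govern: under Table 6 it conflicts at three of five levels, and under Table 8 it directs no dose change for a Grade 4 event, against the plan's own general rules. The conflict is clear at Grades 3 and 4 and softer at intolerable Grade 2.

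The practical size is small, because investigator discretion and the general rules let a careful clinician act. How many subjects would be affected cannot be estimated from the documents. Only toxicity in the irradiated region counts as a DLT, and the dose-escalation rules, primary endpoint, sample size and power do not depend on this row. The conclusion assumes only that the event is judged related to cabozantinib, or of unclear relationship, so that both tables apply. The row should be corrected.

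**What to change.** Amend the stomatitis/mucositis row of Table 8 only, along these lines: *Grade 1 and tolerable Grade 2: no change in cabozantinib. Intolerable Grade 2, Grade 3 and Grade 4: follow Table 6.* Keep the existing oral-care and local-treatment advice for all grades.

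Do not add a general sentence to Section 10.2.2 giving Table 6 precedence. It would disturb rows that depart from Table 6 on purpose, such as those requiring discontinuation at any grade (arterial thromboembolism, perforation or fistula, posterior leukoencephalopathy) and the hematologic row that makes dose changes optional.

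The cost is a wording amendment to one row, with the drug company's approval and IRB submission required by Section 14.4. It adds no visits, procedures or subjects.
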